#### **17. Treatments (if applicable) (include a table for each medication under study)**

Medication 1	Include the corresponding information	No	Does
--------------	---------------------------------------	----	------

			not apply
Name			X
Does it comply with "Good manufacturing practices"?			X
Codes, labeling, storage, retention and storage of medication samples			X
Pharmaceutical form			X
Dose			X
Administration Interval			X
Learn to pronounce Route of administration			X
Administration speed			X
Learn to pronounce Treatment duration			X

#### 18. Follow-up

	Include the corresponding information	No	Does not apply
Number of phases of the study	1		
Number of visits and their schedule (include schedules)	5 scheduled visits in the endocrinology and metabolism department of the National Institute of Medical Sciences and Nutrition Salvador Zubrian. Visits are scheduled between 7:30 a.m. and 2:00 p.m. from Monday to Friday depending on availability.		
Duration of each phase of the study	12 weeks		
Laboratory and cabinet studies that will be used	HbA1c. Fasting blood glucose Lipid profile FGF21. Continuous Glucose Measurement. Insulin		
Total duration of follow-up	12 weeks		
Sampling methods	Serum		
Treatment options to be offered at the end of the study	SGLT2 inhibitors, DPP4 inhibitors, Insulin, GLP1		

#### 19. Overdose Management

N/A

#### 20. Rescue Therapy

SGLT2 inhibitors, DPP4 inhibitors, Insulin, GLP1

## **21. Concomitant therapies allowed**

Oral hypoglycemic agents (Metformin), Aspirin, Blood pressure medications

## **22. Concomitant therapies prohibited**

Insulin

## **23. Definition of monitoring variables**

HbA1c: The measurement of glycosylated Hb is a laboratory test widely used in diabetes to know if the patient's control over the disease has been good during the last three or four months.

Fasting blood glucose

Lipid Profile: A lipid profile is a series of blood tests used to measure the total cholesterol and triglyceride level of an individual.

FGF21: It is produced in the liver in response to high levels of carbohydrates and then enters the bloodstream, where it sends a signal to the brain to suppress the preference for sweets. This is the first hormone derived from the liver that is known to regulate the consumption of sugar in particular

Hunger-Satiety Levels: There are several tables and measurement scales, for practical purposes we will use the scales of the Joslin Institute validated for the Mexican population.

0	3	5	7	10
Ravenous Hunger	Hungry	Satisfied	Full	Very full

1.- On a scale of 1 to 10, being 1 "voracious" and 10 "very full", classify your hunger just before starting to eat.

2.- Halfway through your meal, classify your hunger again using the same scale from 1 to 10. If you are on a "5", "6" or "7" put down your fork and stop eating.

3.- If you decide to continue eating, finish your meal and classify your hunger. Be honest with yourself, too. If you feel you just ate Christmas dinner, but have a huge plate of ice cream in front of you, chances are that you are eating to help deal with some kind of emotion.

## **24. Methods to be used for information collection**

Initial Interview

Initial assessment by specialist doctor and nutritionist.

Follow-up consultation

Data collection sheets

Sheets for weekly food registration.

Databases.

Hunger-Satiety scales.

## **25. Monitoring procedure and audits during the development of the study**

It is a study initiated by the researcher, so Medtronic is not involved in design, monitoring, monitoring, analysis and publication of results.

The department of endocrinology, where advances, problems in the progression of the protocol, will be submitted for evaluation in the research sessions.

## **26. Failure and success criteria**

Success: Corroborate that the effects of a TC3 diet are more beneficial than a conventional TC6 plan. To achieve this, patients should have better glycemic variability, lose more weight, improve fasting blood glucose, improve HbA1c, optimize their lipid level, improve oxidative stress markers and have better control of Hunger-Satiety.

Failure: That the effects of a TC3 diet be equal or less beneficial to the patient's health than a conventional TC6 plan.

**27. Sample size (please include the formula used for the calculation and the source of information on which the assumptions were based)**

a) Sample size

The calculation of the sample size was carried out taking as main outcome the body weight and considering the data of a study in which BMI and weight were evaluated. With these data considering a clinically significant difference, the sample size was calculated in 25 patients per group. A difference in weight 2kg, standard deviation of 2.5, alpha of 0.05 and power of 0.8 were used.

with the following formula:

$$n = 2S^2 (Z\alpha + Z\beta)^2$$

$$\Delta^2$$

Allowing to detect this difference with power of 80% (error  $\beta = 0.20$ ) and with an alpha error of 5%

**28. Description of the techniques, devices and / or instruments that will be used in the measurement (Including: special mechanical, electronic, cybernetic equipment)**

An RJL body composition analyzer with stadiometer will be used.

An ergonomic continuous fiberglass tape measure will be used to measure the circumference of the Seca201® brand body

For the continuous measurement of glucose and glycemic variability, the Medtronic Ipro2 Sensor will be used.

The blood samples will be labeled prior to their inclusion in the "Beckman GPKR Centrifuge" equipment to perform their centrifugation and to be able to separate serum samples, to obtain the laboratories and eppendorf containers will be stored, for each time, to be able to consult later before any situation of doubt Samples will be separated from the tubes to obtain the laboratories.

Beckman-Coulter equipment will be used for the analysis of samples corresponding to blood count.

The Hunger-Satiety scales of the Joslin Institute will be used.

Computing teams of the Department of Endocrinology will be occupied, which have Windows 8.1 pro operating system.

The Easy GV® Software will be used to calculate the glycemic variability indices.

SPSS V21 will be used for data capture and analysis.

**29. Description of the evaluation formats, questionnaires, comparison tables, etc., indicating the validity, reproducibility and quality control criteria that are taken of them**

- General Data Capture Format
- Formats for capturing capillary glycemia.
- Developed for the application in this protocol, with the objective of documenting adverse events.
- Weekly food registration.
- Format for determining physical activities per day and week.
- Hunger-Satiety scale format.

**30. Does the protocol involve the handling and labeling of biological samples? If applicable, mention the procedures that will be used**

Blood samples will be taken 3 times.

Each sample must be centrifuged, to obtain serum and plasma and stored in eppendorf containers.

A label with the following data will be placed in all containers: patient registration number, date, content (plasma, serum, urine), laboratory to be carried out from the sample.

**31. Corresponding information to ensure that the biological samples obtained will not be used for permanent or immortal cell lines or purposes not related to the study**

The samples will be stored, due to the possibility that there is a failure in the trial, or the initiative to measure a new hormone, data that will be included and clarified to the patient in the informed consent.

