## **11. Hypothesis**

1. 1. Weight loss in the TC3 group (Three meal times) will be more significant than in the TC6 group (Six meal times).
2. 2. It will significantly improve glycemic variability in patients undergoing the TC3 regimen.

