## **12. Objetives**

### **Primary objetivo:**

Comparar el impacto en la variabilidad glucémica y pérdida de peso de un régimen alimenticio hipocalórico de tres tiempos (TC3) y un plan convencional de seis tiempos (TC6) en pacientes con DM2 y sobrepeso u obesidad.

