#### **38. Selection criteria**

- a) Inclusion criteria (It must include the definition of the age groups, sex and the severity of the condition that will be allowed in the study)
  - a) Individuals with type 2 diabetes
  - b) Less than 10 years of evolution

c) Age between 40 and 70 years
 
d) Both genders.
 
e) With oral treatment scheme (oral hypoglycemic agents).
 
f) With HbA1c <9%
 
g) With BMI <math>\geq 25</math> to <math><40</math> kg / m^2

b) Exclusion criteria

a) Individuals with another type of diabetes.
 
b) Use of insulin.
 
c) Evolution time of more than 10 years.
 
d) Hospitalization in the last 3 months
 
e) Disease with poor short-term prognosis (for example: cancer)
 
f) Acute infection or febrile syndrome
 
g) Chronic disease other than those to be evaluated, for example: HIV, rheumatic diseases, liver cirrosis
 
h) Pregnancy
 
i) Who do not wish to participate in the study

c) Elimination criteria

a) Men or women who do not wish to continue in the study
 
b) Individuals who do not tolerate the placement of the MCGI
 
c) Individuals who are not attached to the meal plan.
 
d) Individuals who do not respect the corresponding meal times during the study.

39. Outcome and variables

a) Main variables / outcomes to be measured
 
BMI (kg / m^2)
 
a) Weight
 
Glycemic variability, defined with the following indices:
 
a) MAGE (mean amplitude of glycemic excursions)
 
b) MODD (mean of daily differences)
 
c) CONGA-n
 
b) Secondary outcomes to be measured:
 
a) Fasting glucose
 
b) Triglycerides
 
c) Total Cholesterol
 
d) HbA1c
 
e) Oxidative stress
 
f) FGF21
 
g) Systolic and diastolic BP
 
h) Hunger-Satiety Scale
 
a) Frequency of measurements:

Three measurements will be made in a 12-week period with a 6-week interval between each measurement, however the sensor placed in visit 2 will be left for 7 days during which glucose measurements in the interstitial fluid will be obtained every 5 minutes.

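### The success criterion in section 26 requires five outcomes that section 39 classes as secondary, while the primary objective names two outcomes and the 80% power covers weight alone

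*Protocol*

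**What the plan says.** Section 26 of the protocol is headed as failure and success criteria. It frames success as TC3 being more beneficial than TC6, and then lists what is needed: "To achieve this, patients should have better glycemic variability, lose more weight, improve fasting blood glucose, improve HbA1c, optimize their lipid level", followed by "improve oxidative stress markers and have better control of Hunger-Satiety". The last two items are joined by a plain conjunction, so the list reads as cumulative. Failure is defined as "That the effects of a TC3 diet be equal or less beneficial" relative to TC6.

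Other sections set the deciding outcomes differently:

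- Section 11 has two hypotheses. The first is "Weight loss in the TC3 group (Three meal times) will be more significant than in the TC6 group"; the second concerns glycaemic variability.
- The primary objective in section 12 is "Comparar el impacto en la variabilidad glucémica y pérdida de peso", that is, glycaemic variability and weight loss.
- Section 39 gives BMI/weight and the glycaemic-variability indices as main outcomes. Under "Secondary outcomes to be measured" it lists fasting glucose, triglycerides, total cholesterol, HbA1c, oxidative stress, FGF21, blood pressure and the hunger-satiety scale.
- Sections 27 and 42 base the sample size on body weight alone: difference 2 kg, SD 2.5, alpha 0.05, power 0.8, 25 per group.

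The laboratory studies in section 18 are "HbA1c. Fasting blood glucose Lipid profile FGF21. Continuous Glucose Measurement. Insulin".

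**The concern.** The protocol contains three different sets of deciding outcomes: seven in section 26, two in sections 11 and 12, and one in the sample-size sections. Section 26 is the only place that says what counts as success. Applied as written, it would deny success to a trial in which TC3 was superior on both weight and glycaemic variability but, say, HbA1c did not improve. The 80% power in section 42 would then be quoted for a trial whose success criterion it does not describe.

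The seven items are not the full outcome set either. FGF21 and blood pressure stand beside the others in section 39 but are not in section 26, so the list is neither the primary outcomes nor all outcomes.

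One required item may also lack data. Oxidative stress appears in the general variable lists, but no marker is named. It is missing from the laboratory list in section 18 and from every list of blood-sample measurements in section 16 and in the protocol summary before section 8.

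**Working it through.** **1. The plan's own figure.** Inputs from section 42: Δ = 2 kg, S = 2.5, two-sided alpha 0.05 (z = 1.960), power 0.80 (z = 0.842).

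n = 2S²(zα + zβ)²/Δ² = 2 × 6.25 × (2.802)²/4 = 24.53, rounded up to 25 per group.

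The stated sample size reproduces. Sidedness is not stated, but the one-sided formula gives 20, so the two-sided one was evidently used. The figure is correct for weight.

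**2. Which items each section makes decisive.**

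| Item in section 26 | Hypotheses / primary objective (11, 12) | Section 39 | Powered (27, 42) |
|---|---|---|---|
| Weight | yes | main | yes |
| Glycaemic variability | yes | main | no |
| Fasting glucose | no | secondary | no |
| HbA1c | no | secondary | no |
| Lipids | no | secondary (triglycerides, total cholesterol) | no |
| Oxidative stress | no | secondary | no |
| Hunger-satiety | no | secondary | no |

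Five of the seven items are secondary and six of the seven are unpowered. This mismatch needs no assumption.

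**3. What the joined rule could cost (illustration only).** Two assumptions are needed that the protocol does not state: each item must reach two-sided P < 0.05 in favour of TC3, and each has 80% power. The protocol supports 80% for weight only. With test statistics that are normal with common correlation ρ, the chance that all k items succeed is

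P(k) = ∫ Φ[(0.842 + √ρ·u)/√(1 − ρ)]^k φ(u) du, which is 0.80^k at ρ = 0.

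| ρ | All seven | Weight and glycaemic variability | Both of these, but not all seven |
|---|---|---|---|
| 0 | 0.21 | 0.64 | 0.43 |
| 0.3 | 0.36 | 0.67 | 0.31 |
| 0.5 | 0.45 | 0.69 | 0.24 |
| 0.9 | 0.67 | 0.75 | 0.08 |

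The last column is the chance that a trial meets its primary objective and still misses the section 26 criterion. Whatever the power of the other items, the seven-item chance cannot exceed the 0.80 for weight.

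**4. The weaker reading.** If better or improved means only that the estimate points towards TC3, each item succeeds with probability Φ(1.960 + 0.842) = Φ(2.802) = 0.9975 under the same effects, and all seven with 0.9975⁷ = 0.98 at ρ = 0.

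**5. Type I error.** Requiring every item to succeed can only lower the chance of a false claim below that of a single test. The cost of the rule is power.

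**The case against.** The strongest reply is that section 26 is not a decision rule. It names no test, threshold or visit, says only what patients should show, and is not referred to by the outcome, sample-size or analysis sections. Four of its items are worded as improvement without a comparator in that clause, so they could mean change from baseline. This has force against the numbers: moving from 0.21 to 0.98 by redefining one word shows that the joint-power figures illustrate a reading and do not describe the trial. It does not remove the mismatch. The section is titled as the success and failure criteria, its opening sentence compares TC3 with TC6, and nothing else in the protocol says what success is. Under either reading, secondary outcomes decide.

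Three stronger inferences are tempting, and the document does not support them:

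- *The trial has only about 21% power.* That figure needs significance on every item, 80% power on each, and independence. The protocol states none of these for the seven items, and 25 per group is right for weight.
- *The protocol plans to declare the diets equal from a non-significant test.* The failure wording reads naturally as not more beneficial, the complement of success. Section 41 offers only difference tests, but no passage says that equality will be concluded from them. This merits a change of wording and no more.
- *The protocol is deficient because it does not fix the deciding glycaemic-variability index, its visit, or how it combines with weight.* These choices are commonly left to an analysis plan, which is not at hand.

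**Conclusion.** The concern holds as an inconsistency within the protocol. Section 26 ties success to seven items, five of them secondary in section 39, against two outcomes in the primary objective and one in the power calculation. The stated 80% does not describe the section 26 criterion, and one required item, oxidative stress, has no named marker and no place in the listed laboratory work. How much this lowers the chance of success cannot be fixed from the document: 0.21 to 0.67 if all seven must be significant at 80% power each (correlation 0 to 0.9), about 0.98 if only direction counts and the items are independent. The sample size is not wrong for weight, and false-positive risk is not raised. It should be fixed before analysis. Confidence is medium, because section 26 does not define what better means.

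**What to change.** - Rewrite section 26 so that success rests only on the primary outcomes of sections 12 and 39.
- Take fasting glucose, HbA1c, lipids, oxidative stress and hunger-satiety out of the success criterion and report them as secondary, with estimates and confidence intervals.
- State in sections 26 and 42 that the 80% power applies to weight alone.
- As a minor wording change, replace "That the effects of a TC3 diet be equal or less beneficial" with a statement that superiority of TC3 was not shown.

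**Cost.** The change is to wording, and 25 per group can stay. Success can no longer be described as benefit across all seven items. If the sponsor decides that weight and glycaemic variability must both be significant, section 42 must say that the chance of success at 25 per group is about 0.64 to 0.75, not 0.80. That range assumes 80% power for each, correlation 0 to 0.9, and glycaemic variability counted as one endpoint. Restoring 80% for both, with independent endpoints and the same standardised effect of 2/2.5 = 0.8, would need power √0.80 = 0.894 on each, so n = 2 × 6.25 × (1.960 + 1.250)²/4 = 32.2, or 33 per group.

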**32. Description of the treatment groups**

They will be 2 groups each with 25 patients from 30 to 70 years.

One of the groups will have a diet in 3 meal times.

The second group will maintain a diet in 6 meal times.

**33.**

**Mechanisms for treatment allocation**

Random: A reference was generated on randomization.com which is attached.

A Randomization Plan

from

<http://www.randomization.com>

1. a \_\_\_\_\_

2. b \_\_\_\_\_

3. b \_\_\_\_\_

4. b \_\_\_\_\_

5. a \_\_\_\_\_

6. a \_\_\_\_\_

7. b \_\_\_\_\_

8. a \_\_\_\_\_

9. a \_\_\_\_\_

10. b \_\_\_\_\_

11. a \_\_\_\_\_

12. a \_\_\_\_\_

13. a \_\_\_\_\_

14. a \_\_\_\_\_

15. b \_\_\_\_\_

16. b \_\_\_\_\_

17. b \_\_\_\_\_

18. a \_\_\_\_\_

19. b \_\_\_\_\_

20. a \_\_\_\_\_

21. b \_\_\_\_\_

22. a \_\_\_\_\_

23. a \_\_\_\_\_

24. a \_\_\_\_\_

25. b \_\_\_\_\_

26. a \_\_\_\_\_

27. a \_\_\_\_\_

28. a \_\_\_\_\_  
29. a \_\_\_\_\_  
30. a \_\_\_\_\_  
31. b \_\_\_\_\_  
32. b \_\_\_\_\_  
33. a \_\_\_\_\_  
34. b \_\_\_\_\_  
35. b \_\_\_\_\_  
36. b \_\_\_\_\_  
37. b \_\_\_\_\_  
38. b \_\_\_\_\_  
39. b \_\_\_\_\_  
40. b \_\_\_\_\_  
41. b \_\_\_\_\_  
42. a \_\_\_\_\_  
43. a \_\_\_\_\_  
44. a \_\_\_\_\_  
45. b \_\_\_\_\_  
46. a \_\_\_\_\_  
47. b \_\_\_\_\_  
48. b \_\_\_\_\_  
49. a \_\_\_\_\_  
50. b \_\_\_\_\_

50 subjects randomized into 1 block

To reproduce this plan, use the seed 6312

along with the number of subjects per block/number of blocks

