## **13. Methodology: General design.**

### a) Study design:

It is a simple blind randomized clinical trial (Information Analyst) in which a group of patients with DM2 and overweight or obesity will be subjected to a 3-course low-calorie diet (TC3), and another to a conventional hypocaloric regimen of 6 meal times (TC6) over a period of 14 weeks with the objective of evaluating the benefits, differences and impact on the health of patients, comparing weight loss, glycemic variability, HbA1c, glycemia, lipid profile , oxidative stress, FGF-21, Blood pressure and Hunger-Satiety level.

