### d) Treatment allocation mechanism (random / open): Random

### e) Treatment groups

It is intended to include two groups of patients with type 2 diabetes mellitus between 40 and 70 years old who meet all the inclusion criteria.

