### f) Duration of individual follow-up

12 weeks			
14. Temporality of the study.			
Type of study		Select an option	
Retrospective			
Prospective		X	
15. Process of assigning the groups under study			
Maniobra	Yes (Include the corresponding information)	No	does not apply
Randomization	X		
Open study			
Simple blind study	X		
Double blind study			
Triple blind study			
16. Descripción de las maniobras o las intervenciones			
50 patients with DM2 will be recruited from the Institute's Diabetes clinic who are overweight or obese and who are between 40 and 70 years old and who are with oral hypoglycemic agents, with an HbA1c less than 9% and who are less than 10 years old of evolution			
Clinical evaluation			
A complete medical history and physical examination will be performed in order to confirm the presence of the inclusion criteria and rule out the presence of exclusion criteria. An anthropometric evaluation and body composition (waist and hip circumference, height, weight and percentage of fat) will be made, as well as blood pressure measurement. An interrogation will be conducted to document a history of coronary heart disease, menopausal status and use of hormonal therapy, smoking, alcohol consumption and physical activity (through a validated physical activity questionnaire in the Mexican population).			
Nutritional assessment.			
Will be performed			
Patients will be divided into 2 groups without distinction.			
. The first group that will be 25 patients will undergo a hypocaloric regimen with caloric restriction of 15% of their usual daily consumption with a distribution of macronutrients of 40% in Carbohydrates, 20% of Protein and 40% of Lipids in three times of food (TC6) during a period of 12 weeks in which the following variables will be measured (Weight, Glycemic Variability: Monitor, HbA1c, Glycemas, Lipid Profile, Oxidative, FGF-21, Blood Pressure and Hunger-Satiety levels.)			

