During the first visit, the clinical evaluation will be developed, which consists of a complete physical examination in which vital signs, neck and head examination, chest and abdomen examination, upper and lower limb examination will be measured. As well as a complete nutritional assessment that includes, anthropometric assessment by segments using dry label tape measure, dry brand pellotrometer and dry brand anthropometry; Body composition assessment using impedance OMRON model 512, 72hrs food consumption reminder to collect information on the feeding of each patient. Based on the information collected, the individualized TC6 plan will be prescribed and a 24/7 reminder format will be delivered to be filled out by the patient for a week, in addition to giving the indication to perform a blood glucose measurement at home once a day. in random scheme.			
To assess the adherence to the nutritional plan, the patient will be summoned 15 days later to perform daily			

consumption assessment using the 24/7 reminder format filled out by the patient and a 72hrs reminder made through an interview. Also, Hunger-Satiety levels will be measured with the Joslin institute tables validated for the Mexican population

If the patient adheres to the diet, blood samples will be taken to measure the variables (HbA1C, Glucose, Lipid Profile, Insulin, FGF-21) and after that place the continuous glucose monitor Medtronic model Ipro2 with in order to monitor the patient's blood glucose for 7 days.

At the end of 7 days, the patient will be summoned to remove the sensor and re-evaluate the diet.

The TC6 plan will be continued for 6 weeks, and at the end of this period the patient will be summoned again to perform blood samples to measure the variables (HbA1C, Glucose, Lipid Profile, Insulin, FGF-21), Weight, Blood pressure and hunger-satiety levels.

The TC6 regime will continue for another 6 weeks. At the end of the period, the patient will be cited to re-perform blood samples to measure the variables (HbA1C, Glucose, Lipid Profile, Insulin, FGF-21), Weight, Blood Pressure and Hunger-Satiety levels

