The second group that will be 25 patients will undergo a hypocaloric regimen with caloric restriction of 15% of their usual daily consumption with a macronutrient distribution of 40% in Carbohydrates, 20% Protein and 40% of Lipids in three times of food (TC3) during a 12-week period in which the following variables will be measured (Weight, Glycemic Variability: Monitor, HbA1c, Glycemia, Lipid Profile, Oxidative, FGF-21, Blood Pressure and Hunger-Satiety levels. )

During the first visit, the clinical evaluation will be developed, which consists of a complete physical examination in which vital signs, neck and head examination, chest and abdomen examination, upper and lower limb examination will be measured. As well as a complete nutritional assessment that includes, anthropometric assessment by segments using dry label tape measure, dry brand ptyometrometer and dry brand anthropometry; Body composition assessment using impedance OMRON model 512, 72hrs food consumption reminder to collect information on the feeding of each patient. Based on the information collected, the individualized TC3 plan will be prescribed and a 24/7 reminder format will be delivered to be filled out by the patient for a week, in addition to giving the indication to perform a blood glucose measurement at home once a day. in random scheme.

To assess the adherence to the nutritional plan, the patient will be summoned 15 days later to perform daily consumption assessment using the 24/7 reminder format filled out by the patient and a 72hrs reminder made through an interview. Also, Hunger-Satiety levels will be measured with the Joslin institute tables validated for the Mexican population.

If the patient adheres to the diet, blood samples will be taken to measure the variables (HbA1C, Glucose, Lipid Profile, Insulin, FGF-21) and after that place the continuous glucose monitor Medtronic model Ipro2 with in order to monitor the patient's blood glucose for 7 days.

At the end of 7 days, the patient will be summoned to remove the sensor and re-evaluate the diet.

The TC3 plan will be continued for 6 weeks, and at the end of this period the patient will be summoned again to perform blood samples to measure the variables (HbA1C, Glucose, Lipid Profile, Insulin, FGF-21), Weight, Blood pressure and hunger-satiety levels.

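### Section 33 prints the complete ordered allocation list and its seed in the protocol, with no concealment step described, so upcoming assignments may be readable before enrolment

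*Protocol*

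**What the plan says.** Section 33 of the protocol (Mechanisms for treatment allocation) states "A reference was generated on randomization.com which is attached" and reproduces the output: entries 1 to 50 in order, each coded a or b. Below the list stand "50 subjects randomized into 1 block" and "To reproduce this plan, use the seed 6312". The section does not say which code is the three-meal diet (TC3) and which the six-meal diet (TC6).

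The other statements on allocation are short. Section 13(d) reads "Treatment allocation mechanism (random / open): Random", section 15 ticks randomisation, and section 16 says "Patients will be divided into 2 groups without distinction". Section 13(a) calls the trial single-blind and names the information analyst as the blinded party. The diets themselves are open: at the first visit, according to section 16, "Based on the information collected, the individualized TC6 plan will be prescribed" in one group and "Based on the information collected, the individualized TC3 plan will be prescribed" in the other.

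The protocol text reviewed does not mention sealed envelopes, central release, a list holder or restricted access to the list.

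**The concern.** Randomisation protects the comparison only if whoever decides on enrolment cannot know the next assignment. Here the document that study staff would normally work from contains the whole sequence and the means to regenerate it. Someone who can read ahead can delay, hasten, invite or decline a patient according to the diet that comes next. For example, entries 34 to 41 are eight consecutive b assignments.

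Blinding the analyst does not address this, because the risk arises at enrolment. The planned analysis does not address it either: section 41 compares the groups with a t-test or Mann-Whitney test without adjustment, so it relies on randomisation alone to make the groups comparable.

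**Working it through.** **Is the printed list the operating list?** It has 50 entries, 25 a and 25 b. Section 43 plans 25 patients per diet. Sections 27 and 42 use a difference of 2 kg, SD 2.5, alpha 0.05 and power 0.80, and this reproduces: n = 2 × 2.5² × (1.960 + 0.842)² / 2² = 24.53, rounded up to 25 per group. The list therefore matches the whole planned trial and is not a sample of the method.

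**Predictability with the list hidden.** Suppose a recruiter knows past assignments (the diets are open) and always guesses the arm with more places left. For one balanced block of 2m, the expected number of correct guesses is m + (2^(2m)/C(2m, m) − 1)/2.

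- m = 25: 25 + (8.907 − 1)/2 = 28.953 of 50.
- The first guess is a coin toss (0.5), leaving 28.453 of the next 49, or 58.1%.

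**Predictability with the list in hand.** Two codes need one link: once one patient's diet is matched to one entry, every other entry is decoded. If that happens at entry 1, 49 of 49 later assignments are readable. The extra exposure from printing runs from 0 (recruiters never see the list) to 49 − 28.453 = 20.547, about 20.5 assignments. The exposure comes from the printing and not from the block size.

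**What a mid-trial switch would cost.** The running a-minus-b difference in the printed list is 0 after entries 2, 6, 8, 10, 40, 42, 48 and 50. It is +4 after entry 14 (9/5) and largest, at +8, after entry 30 (19/11). With a new balanced list for the remaining patients:

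- switch after entry 14: 9 + 18 = 27 and 5 + 18 = 23;
- switch after entry 30 (worst case): 19 + 10 = 29 and 11 + 10 = 21.

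Power for 2 kg, SD 2.5, two-sided 0.05, is Φ(2 / (2.5 √(1/n₁ + 1/n₂)) − 1.960):

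| Split | Normal approximation | Noncentral t |
|---|---|---|
| 25/25 | Φ(2.828 − 1.960) = 0.807 | 0.791 |
| 27/23 | Φ(2.819 − 1.960) = 0.805 | 0.789 |
| 29/21 | Φ(2.792 − 1.960) = 0.797 | 0.781 |

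**Alternative: permute the places left so that the trial ends at 25/25.** After entry 30 there are 6 a and 14 b places left. The recursion f(a,b) = max(a,b)/(a+b) + [a f(a−1,b) + b f(a,b−1)]/(a+b), with f(a,0) = a and f(0,b) = b, gives 14.56 of 20 correct guesses (72.8%). A new 10/10 list gives 10 + (5.676 − 1)/2 = 12.34 of 20 (61.7%). After entry 14 the figures are 21.9 of 36 (60.8%) and 21.3 of 36 (59.1%). The new 1:1 list is harder to guess at both points.

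**The case against.** The strongest reply is that the protocol does not show anyone could use the list. It does not say who holds it, whether patients are entered in list order, or which diet is a. Copies containing section 33 may have been restricted, or a different working list used. Some front pages were not in the text available for this review, so a concealment statement there cannot be strictly excluded. Most eligibility criteria in section 38 are measured or documented, which narrows the room for selective refusal. The extra exposure has a lower bound of zero.

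This limits the claim to a risk, and the finding goes no further. The a/b coding is weak protection, since one linked patient breaks it. Documented eligibility criteria do not prevent steering by timing or invitation. An unwritten envelope procedure would not help against a recruiter who has the protocol, because the order and seed are in its text. Nor could a separate analysis plan undo the printing.

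Three practical objections also have force. The replacement list must be balanced, or the 29/21 bound fails. Baseline must mean the first-visit assessment, because the first described blood samples and the glucose sensor come about 15 days after the diet is prescribed. And the protocol names no one outside recruitment who could hold the list.

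**Conclusion.** The point holds. The protocol fixes the allocation mechanism badly: followed as written, it leaves upcoming assignments open to anyone holding the document, in a trial with open diets. The upper bound of 49 of 49 assumes that enrolling staff hold the protocol, that patients enter in list order, and that the first patient's diet is linked to entry 1.

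The document does not show that selective enrolment took place, and any effect on weight or glycaemic variability cannot be estimated from it. The case for change is that a core safeguard is missing and cheap to restore. Confidence is medium, because custody of the list and recruitment status are not stated.

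**What to change.** Take the list and seed out of the protocol and describe concealment in section 33. For patients not yet randomised, generate a new balanced 1:1 list with an unpublished seed, held by someone outside recruitment. This should not be the information analyst, if a diet-linked list would unblind that person. Release each assignment only after consent and the first-visit baseline assessment, by sequentially numbered opaque sealed envelopes or a password-held list.

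- **No patient allocated yet:** a new list of 50 ends at 25/25.
- **Some allocated:** use a new balanced list for the rest and accept the imbalance, in preference to permuting the remaining places.
- **All allocated:** only the reporting below applies.

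In every case, report how many patients were allocated from the printed list and that no concealment of it was described.

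The cost is one new list, its custody and a short amendment. The total stays at 50 and no patient procedure is added. This assumes that existing staff outside recruitment can hold the list. The worst-case loss of power, about 0.01 at 29/21, assumes that patients so far were entered in printed order and that all 50 are analysed.
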